repeated measures correlation of 0.50, an effect size of $f=0.35$, a two-way $\alpha=0.05$, and a power of $1-\beta=0.80$, the required total sample size was calculated as $N=46$ (23 participants in each group). Considering possible attrition, a total sample size of 30 participants was planned for each group. Accordingly, 58 volunteer students were recruited for the quantitative phase and randomly assigned to either the intervention or control groups. For the qualitative phase, 12 students were purposively selected from among those who had participated in the quantitative phase. In addition, nurse educators with at least five years of experience in teaching and mentoring students were included as participants. Data collection for the qualitative phase was carried out through focus group interviews and continued until no new themes emerged, indicating thematic saturation.

Randomisation and Blinding

Eligible participants were randomly assigned to either the experimental group, which received the digital escape room game intervention, or the control group, which received traditional classroom-based education, in a 1:1 allocation ratio. Randomisation was performed using an online random sequence generator (Research Randomizer, <https://www.randomizer.org/>) by an independent statistician who was not involved in participant recruitment, intervention delivery, or outcome assessment.

Given the nature of the interventions, blinding of participants and facilitators was not feasible. However, to minimise performance and detection bias, outcome assessors and data analysts remained blinded to group allocation throughout the study. All data were coded anonymously, and statistical analyses were conducted using coded identifiers (Group A/Group B) until the final interpretation phase.

Pre-application of the study

A preliminary application was undertaken to assess the clarity, feasibility, and functionality of both the data collection instruments and the digital escape room game. This

stage was conducted with 10 fourth-year nursing students enrolled in the 2024–2025 academic year. Participants were asked to complete the data collection forms, engage with the escape room game, and provide structured feedback regarding the comprehensibility of the forms, the usability of the game design, and the alignment of tasks with the intended learning outcomes.

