Based on the feedback obtained, minor revisions were made to enhance the precision of the data collection tools and to optimize the flow and instructional components of the game. Following these adjustments, both the instruments and the game were finalized for the main study. To maintain methodological rigor and avoid potential bias, students who participated in the pre-application were excluded from the final sample.

Implementation phase of the study

All students who agreed to participate first completed the Sociodemographic Information Form, followed by the Hypovolemic Shock Information Form as a pretest. After the pretest, all participants received a two-hour traditional lecture on hypovolemic shock and nursing management. The lecture covered the following topics: definition, etiology and risk factors, pathophysiology, clinical findings and diagnosis, medical treatment approaches, nursing care and processes, nursing diagnoses and interventions, patient education, and psychosocial support. Students were then randomly assigned to either the intervention or control group, ensuring comparable mean pretest knowledge scores.

Control Group (n = 28): In addition to the two-hour theoretical training, no further intervention was provided. Immediately after the lecture and again one month later, students completed the Hypovolemic Shock Information Form as a posttest. After completion of the study, control group participants were also given the opportunity to experience the digital escape room game.

Intervention Group (n = 27): Following the pretest and theoretical training, students played a digital escape room game on hypovolemic shock and nursing management developed

by the researchers using the *Genially* platform. The design and procedures of the game are detailed in the “Experimental procedure” section. Immediately after the intervention and again one month later, students completed the Hypovolemic Shock Information Form as a posttest. In addition, the GAMEX (Game Experience) Scale was administered, and a subset of students participated in a focus group interview.

Experimental procedure

This study was conducted with third-year undergraduate nursing students to evaluate knowledge and management of hypovolemic shock. It comprised two stages: (1) development and implementation of the HYPSEM ERG, and (2) testing the game and assessing outcomes.

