of the discussions. The interview form consisted of four open-ended questions addressing participants' expectations prior to the game and whether these were fulfilled, the emotions they experienced during the activity, the game's contribution to their learning (e.g., knowledge, practical skills, decision-making), and their opinions on the broader use of digital escape room games in nursing education. The discussions explored not only students' experiences and perceptions of the usefulness of the HYPSEM game, but also their suggestions for areas of improvement. Each focus group included three to five participants and lasted between 45 and 80 minutes. All sessions were audio-recorded and subsequently transcribed verbatim.

Statistical Analysis Plan (SAP):

Quantitative data analyses were conducted using IBM SPSS Statistics version 25. Descriptive statistics (mean, standard deviation, minimum, and maximum) were calculated for all study variables. The internal consistency of the GAMEX scale and its subdimensions was assessed using Cronbach's α coefficients.

To evaluate baseline equivalence between groups, independent samples t -tests were performed. The effectiveness of the intervention over time was examined using a repeated-measures analysis of variance (ANOVA) with one within-subjects factor (time: pre-test, post-test 1, post-test 2) and one between-subjects factor (group: GAMEX vs. control). Mauchly's test of sphericity was applied to verify the assumption of sphericity, and where violations occurred, the Greenhouse-Geisser correction was used. Effect sizes for ANOVA results were reported as partial η^2 .

In addition, Bonferroni-adjusted pairwise comparisons were conducted to explore differences across the three time points within each group. Independent samples t -tests were also carried out at each measurement point to assess between-group differences. For these comparisons, Cohen's d values were calculated to estimate the magnitude of differences (0.2 = small, 0.5 = medium, 0.8 = large). Statistical significance was set at $p < .05$ for all analyses.

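### The protocol does not say whether or how pretest scores were used in allocation, and the planned between-group tests leave pretest out as a covariate

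*Combined protocol and SAP*

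**What the plan says.** Randomisation and Blinding says that assignment was made "in a 1:1 allocation ratio" and that "Randomisation was performed using an online random sequence generator", by a statistician independent of recruitment, delivery and outcome assessment. It mentions no stratification, blocking, matching, minimisation or use of scores.

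Implementation phase of the study gives the order of events. The pretest came first; then "After the pretest, all participants received a two-hour traditional lecture on hypovolemic shock and nursing management"; then "Students were then randomly assigned to either the intervention or control group, ensuring comparable mean pretest knowledge scores". It names no method, no tolerance and no holder of the scores.

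Setting and participants says that "58 volunteer students were recruited for the quantitative phase and randomly assigned to either the intervention or control groups". The group sizes given later are 28 (control) and 27 (intervention), 55 in all.

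The SAP says: "To evaluate baseline equivalence between groups, independent samples t -tests were performed". Its main analysis is a repeated-measures ANOVA with pretest as the first of three levels of time and group as the only between-subjects factor. It adds unadjusted t-tests at each time point. It specifies no baseline covariate, stratum or pair term. The power calculation is for the between-group effect.

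**The concern.** The two accounts of allocation do not fit together as written. A sequence drawn without regard to scores balances pretest means on average over many draws; it does not guarantee balance in the draw that was used. Because the pretest preceded assignment, the scores could have been available, so the text leaves two possibilities:

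- The balance clause loosely describes an expected or observed result, and no scores were used. The clause is then wrong as a description of the method.
- Scores were used, by redrawing, stratifying or matching. The method section is then incomplete, and the SAP analyses the data as if allocation had been unrestricted.

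The first is a matter of accurate reporting. The second also affects the analysis. Balancing on a variable that predicts the outcome makes the true sampling variance of the group difference smaller than an unadjusted test estimates. Standard errors are then too large, and the trial loses power it could have kept with data it already holds.

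**Working it through.** **The plan's own figure.** Inputs from Setting and participants: f = 0.35, m = 3 time points, correlation 0.50, alpha 0.05, power 0.80. For the between-group effect, lambda = f² × N × m / (1 + (m − 1) × rho), with 1 and N − 2 degrees of freedom.

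- N = 46: lambda = 0.1225 × 46 × 3 / 2 = 8.45, power 0.811.
- N = 44: lambda = 8.09, power 0.793.

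The stated N = 46 is reproduced. It is not in dispute; it matters here only because it shows that the trial was sized on the group main effect.

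**Can a sequence that ignores scores ensure comparable means?** Assume the 58 students split 29 and 29.

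- SE of the pretest difference in SD units = sqrt(1/29 + 1/29) = 0.263.
- P(difference above 0.20 SD) = 2 × (1 − Phi(0.20/0.263)) = 0.45.
- P(above 0.25 SD) = 0.34; P(above 0.50 SD) = 0.06.

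With 28 and 27 the SE is 0.270, and a gap above 0.20 SD occurs in 46% of draws. So the answer is no.

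**What follows if allocation was constrained on pretest?** Assume that lists were redrawn until the means agreed within 0.10 SD. This tolerance is not in the documents. Assume normal scores with equal correlation between time points.

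1. The limit is 0.10/0.263 = 0.38 standard errors. A normal variable truncated at ±0.38 keeps a fraction v = 0.047 of its variance.
2. For a summary whose squared correlation with pretest is R², the test statistic has SD of about sqrt(1 − R² × (1 − v)) instead of 1.
3. Post-test t-test, rho = 0.5: R² = 0.25, so SD = sqrt(1 − 0.25 × 0.953) = 0.873. Then 1.96/0.873 = 2.25, a true size of about 2.5%.
4. Group main effect, averaged over three times: R² = (1 + 2 × 0.5)/3 = 0.667, so SD = sqrt(1 − 0.667 × 0.953) = 0.604. Then 1.96/0.604 = 3.24, a true size of about 0.1%.

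Null simulation (29 per arm, 20,000 runs per row, redraw rule as above) agrees. Repeat runs at rho = 0.5 gave 2.4% to 2.5% for the post-test t-test.

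| rho | post-test t-test | group main effect | pre–post change | pretest as covariate |
|---|---|---|---|---|
| 0.3 | 4.2% | 0.5% | 1.8% | 5.1% |
| 0.5 | 2.5% | 0.1% | 2.5% | 5.1% |
| 0.7 | 0.6% | about 0% | 3.4% | 4.9% |

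Pair matching on pretest gives nearly the same figures. Stratifying at the median is milder: about 3.1% for the post-test t-test at rho = 0.5. Under unrestricted allocation all four tests hold about 5%.

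**The pretest t-test.** Under the 0.10 SD rule its statistic cannot exceed about 0.38 in absolute value, so it cannot reject. That is true by construction.

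**The case against.** A reader might infer that scores were definitely used. The documents do not support that. The clause may be loose wording for balance that was expected or observed afterwards. The SAP still tests baseline equivalence, which would be largely redundant had balance been forced. The protocol also does not call the sequence simple or unrestricted: generator output can be applied within score strata or pairs, so this could be under-reporting rather than contradiction. This objection stands, and the point is therefore put as two possibilities.

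A reader might go further and infer that students were moved between groups by hand. Nothing in the documents says so, and the list is attributed to an independent statistician. That reading is conjecture.

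The harm that can be sized also runs in the safe direction: conservative tests, not false positives. Pretest is not wholly ignored either, since it is a level of time in the ANOVA and a group-by-time contrast uses it. Both remarks are right. But the change contrast is also conservative under constrained allocation (1.8% to 3.4% in the table), and the main effect on which the trial was sized is the worst affected.

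Finally, 58 were assigned and the stated groups total 55, so balance set at assignment need not hold among those analysed. That is one more reason to adjust for pretest rather than rely on a claim of balance.

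**Conclusion.** The two protocol sections are unreconciled and need correction whichever possibility is true. The claim that means were ensured to be comparable cannot rest on a sequence that ignores scores: a gap above 0.20 SD is close to an even chance (45%).

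Whether the analysis is affected depends on an undisclosed fact. If no scores were used, the planned tests have correct size, though they forgo the precision that pretest offers. If scores were used, the unadjusted tests are too conservative: at correlation 0.5, about 2.5% for the post-test t-test and 0.1% for the group main effect, instead of 5%. These sizes rest on the assumed 0.10 SD redraw rule, 29 per arm and normal scores; only the correlation of 0.5 is the protocol's. A looser scheme gives a smaller effect. A pretest-adjusted comparison holds about 5% in either case, so the analysis can be put right without first settling what happened.

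**What to change.** 1. **Analysis.** At the two post-tests, compare the groups with a model for the post-test scores that has group and pretest score as a covariate, plus any stratum or pair used in allocation. Use it in place of the unadjusted post-test t-tests and the group main effect averaged over pretest. It is valid under simple or restricted random allocation. Under simple allocation it also gains precision: at correlation 0.5 the residual variance falls to 1 − 0.5² = 0.75 of the unadjusted value.
2. **Allocation text.** The allocation is already made, so describe it rather than write a new rule. State in both sections the step actually used, who held the pretest scores, any redraws (criterion and number) and any moves. If no scores were used, delete the clause about comparable pretest means.
3. **Baseline.** Report pretest mean and SD by arm, and do not rely on the pretest t-test as evidence of equivalence.

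The cost is one covariate that has already been collected, one degree of freedom, and edits to two protocol sections and the SAP. The report may have to disclose a redraw or a move. If any student was moved by hand, adjustment for pretest does not repair that, and disclosure is what lets a reader judge it.

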Stage 1: The HYPSEM (HYPovolemic Shock EMergencies) ERG was developed, introduced to students, and made available for one week.

Stage 2: Upon completion, students’ knowledge and satisfaction were evaluated.

HYPSEM game procedure

HYPSEM is a web-based digital escape room addressing hypovolemic shock (HVS). It was designed to examine whether escape rooms enhance motivation to learn about HVS. Development on the *Genially* platform enabled the creation of interactive click-and-point rooms, fostering engagement. Hosting the game online ensured universal access without spatial or temporal constraints.

Implementation proceeded as follows:

- Students first received a face-to-face briefing in which the designer introduced escape rooms, explained the *Genially* platform, and outlined the collaborative structure of the game.
- They were then given one week to play individually at their convenience.

- The designer shared contact information to provide technical support. Students could request unlimited hints and were reassured that feedback would be available even without prior experience.
- After successfully completing the final test and exiting the escape room, students filled out a post-test questionnaire.

Escape room design

HYPSEM simulates a hospital room scenario involving a patient with hypovolemic shock, requiring students to access essential information from the patient's file to prevent adverse outcomes. The game can be accessed via *Genially* (<https://view.genially.com/685bc3f26dbc4e0ec352beb0/interactive-content-hastaneden-kacis-oyunu>).

Students had 15-20 minutes to solve six puzzles. Content aligned with prior lectures, practice sessions, and case studies; no new information was introduced during gameplay to facilitate smooth progression. Access was provided via QR code. The game opened with a clinical narrative, followed by rules, instructions, and symbol explanations.

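### Post-test 1 follows the lecture at once in controls but follows a self-paced game with a one-week window in the intervention arm, so the contrast there mixes the game with elapsed time

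*Combined protocol and SAP*

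**What the plan says.** Under *Implementation phase of the study*, all participants take the pretest and then the same two-hour lecture. The two arms are then tested on different clocks:

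- Control group: "Immediately after the lecture and again one month later, students completed the Hypovolemic Shock Information Form as a posttest".
- Intervention group: "Immediately after the intervention and again one month later, students completed the Hypovolemic Shock Information Form as a posttest".

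The intervention is not a fixed session. *Experimental procedure* (Stage 1) says the game was "introduced to students, and made available for one week", and *HYPSEM game procedure* adds "They were then given one week to play individually at their convenience". *Escape room design* gives the length of play ("Students had 15-20 minutes to solve six puzzles") and allows unlimited replay during the week.

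Two sentences bear on what triggers the intervention arm's test. Stage 2 has "Upon completion, students’ knowledge and satisfaction were evaluated". *HYPSEM game procedure* has "After successfully completing the final test and exiting the escape room, students filled out a post-test questionnaire".

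The SAP uses a three-level time factor shared by both arms (pre-test, post-test 1, post-test 2), within-group pairwise comparisons over time, and an independent t-test between arms at each measurement point. It sets no test window and does not use actual test dates.

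**The concern.** The game reinforces lecture content and adds nothing new (*Escape room design*), so the score depends partly on how well the lecture has been retained. Controls are measured when the lecture is freshest. Intervention students are measured after a delay that most of them choose for themselves. Two things other than the game can act during that delay: forgetting, which works against the game, and study unrelated to it, which works in its favour. Randomisation balances the students but not a test schedule that differs by arm.

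Study prompted by the game is a different matter and can fairly count as part of its effect, since the protocol says of the game: "It was designed to examine whether escape rooms enhance motivation to learn about HVS".

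Three results are exposed: the t-test at post-test 1 with its Cohen's d, the group-by-time interaction, and the change from post-test 1 to post-test 2, which a reader would take as retention.

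**Working it through.** **1. Lag from lecture to post-test 1.** Controls: about 0 days. Intervention arm: 0 to 7 days if the game briefing was on the lecture day, and longer by any gap between lecture and briefing, which is not stated. *Data collection* gives June 2 to July 20, 2025, which is 48 days. If one month means 30 days after post-test 1, the calendar caps the lag at 48 − 30 = 18 days. That is a ceiling, not evidence of such a delay.

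**2. Post-test 2.** The starting point of the month is not stated. With the briefing on the lecture day and a month of 30 days:

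| Month counted from | Lecture to post-test 2, control v intervention | Post-test 1 to post-test 2, control v intervention |
|---|---|---|
| own post-test 1 | 30 v 30–37 days | 30 v 30 days |
| lecture | 30 v 30 days | 30 v 23–30 days |

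Either reading leaves one mismatch, and a lecture-to-briefing gap widens it.

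**3. The plan's own sample size.** Inputs from *Setting and participants*: f = 0.35, m = 3 measurements, ρ = 0.50, α = 0.05, between-group effect. Noncentrality λ = f²·N·m / (1 + (m − 1)ρ). At N = 46, λ = 0.1225 × 46 × 3 / 2 = 8.45, giving power 0.811. At N = 44 power is 0.793. The stated N = 46 reproduces. It is powered for the between-group main effect.

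**4. What a shift would do.** The documents give no figure, so shifts s of 0.1, 0.2 and 0.3 SD are assumptions. Inputs: 28 controls and 27 intervention students, ρ = 0.50, two-sided 5%, sphericity, h = 28 × 27 / 55 = 13.745. The shift acts at post-test 1 only, so with no game effect the arm differences at the three times are (0, s, 0).

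- t-test at post-test 1: SE = √(1/28 + 1/27) = 0.270 SD, 53 df, critical value 2.006, noncentrality s/0.270.
- Interaction, F(2, 106): noncentrality h × (2s²/3) / (1 − 0.50) = 0.183, 0.733, 1.649.
- Main effect, F(1, 53): variance of the three-point mean (1 + 2 × 0.50)/3 = 0.667; noncentrality h × (s/3)² / 0.667 = 0.023, 0.092, 0.206.

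| Assumed shift | t-test | Interaction | Main effect |
|---|---|---|---|
| none | 5% | 5% | 5% |
| 0.1 SD | 6.5% | 6.4% | 5.3% |
| 0.2 SD | 11.3% | 10.8% | 6.0% |
| 0.3 SD | 19.4% | 18.8% | 7.3% |

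Simulation with 40,000 runs agrees for the interaction (6.4%, 10.9%, 18.7%) and the main effect (5.3%, 6.1%, 7.1%).

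**5. Direction.** These are two-sided rates. If the shift is net forgetting, the chance of falsely declaring the game better falls from 2.5% to 1.0%, 0.4% and 0.1%, and the extra rejections favour control. If it is net unrelated study, the two are mirrored.

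**6. Power under an adverse 0.2 SD shift.** The plan's effect is 2f = 0.70 SD.

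| Analysis | True arm differences (pre, post 1, post 2), SD | No shift | Post-test 1 reduced by 0.2 SD |
|---|---|---|---|
| t-test at post-test 1 | 0.70 at post-test 1 | 72% | 44% |
| Main effect | 0.70, 0.70, 0.70 (the plan's model) | 88% | 81% |
| Main effect | 0, 0.70, 0.70 | 55% | 43% |
| Interaction | 0, 0.70, 0.70 | 76% | 65% |

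The 55% baseline in the third row comes from averaging in a pre-test with no difference. It is not a consequence of the timing.

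**The case against.** The strongest reply is that each arm is tested at the end of its own teaching, with the access week and replay as part of what is offered. That is a coherent pragmatic question. The plan, however, does not state it as its question; it states an effect of the intervention on knowledge and treats post-test 1 as one time point.

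Several further points limit the weight of the concern:

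- A student who plays on the lecture day has almost no lag. The documents permit a delay but do not show one.
- No size is documented, and 0.3 SD over 0 to 7 days may be too large. If forgetting dominates, the bias runs against the game and a false claim in its favour becomes less likely (step 5).
- The two sentences on the test trigger can be read as agreeing that each student was tested on leaving the game. If so, permitted replay could continue after post-test 1, which further blurs the change between post-tests.
- The main effect is spared only if the shift stays at post-test 1. An equal shift at both post-tests, an upper bound, gives noncentrality h × (2s/3)² / 0.667 = 0.092, 0.367, 0.825 and rejection rates of 6.0%, 9.1% and 14.5%. This makes the main effect less protected than the table in step 4 suggests.

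These points govern how firmly the size can be stated. None of them removes the difference in schedule or supplies a correction in the SAP.

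**Conclusion.** The concern holds and should be fixed. That the arms are tested on different clocks is plain from the text and needs no assumption. As planned, the post-test 1 t-test, the interaction and the post-test 1 to 2 change estimate the game plus elapsed time.

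The size and net direction are unknown. Under assumed shifts of 0.1 to 0.3 SD confined to post-test 1, the false-positive rate is 6.5% to 19.4% for the t-test and 6.4% to 18.8% for the interaction, against 5.3% to 7.3% for the main effect. The stated sample size is unaffected.

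**What to change.** **By design.** Give post-test 1 to all randomised students on one common date at the close of the game window, and post-test 2 on one common date a month later. The cost is rescheduling one 20-item test. What is lost is the controls' day-0 score and the immediate post-game score, and players would be tested 0 to 7 days after play. Controls would also wait a week while peers hold the game, a small added contamination risk that the plan already accepts for post-test 2.

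**If the data are already collected**, as the June 2 to July 20, 2025 collection dates imply:

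1. State what the month to post-test 2 is counted from, and whether intervention students were tested on leaving the game or after the window closed.
2. Report days from lecture to each test, by arm.
3. Describe the post-test 1 difference and the post-test 1 to 2 change as game plus elapsed time.
4. Put the emphasis on the post-test 2 comparison, label that choice as post hoc because no primary time point was named, and note any remaining offset.

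Do not adjust for days since the lecture. Controls have no spread in lag, and if all intervention students were tested when the window closed, lag is fully collinear with arm.

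This fallback costs only reporting of dates and rewording. It leaves the post-test 1 contrast uncorrected.

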The puzzles included multiple-choice, true/false, sequencing, and clinical reasoning tasks related to shock type, stage, management, and nursing interventions. Clues were drawn from patient files, physical examination findings, laboratory results, and vital signs. Incorrect responses triggered warning signals as feedback. A countdown timer imposed time constraints, and hints were embedded in items such as the patient file, behind a door, an electrocardiograph, a medication bag, and above a cupboard. Successful management of the patient and hospital exit designated students as “heroes.” Students could replay the game without restriction during the one-week study period.

Data collection

Data were collected face-to-face and via Google Forms between June 2 and July 20, 2025. In this study, multiple instruments were employed to assess students' knowledge of shock management, their satisfaction with the game, and their perceptions of the digital escape room.

Quantitative data

Sociodemographic Information Form

Sociodemographic data, including participants' age, gender, and prior experiences, were collected using a form developed by the researchers based on the literature (Bonaduce, 2024; Sat et al., 2025).

Hypovolemic Shock Information Form

A 20-item true-false test was administered to measure students' theoretical knowledge of hypovolemic shock. The form was reviewed by seven field experts to establish content validity and was administered both as a pretest and a posttest.

GAMEX (Game Experience) Scale

Students' experiences with the digital escape room were evaluated using the 27-item, 5-point Likert-type GAMEX scale (Eppman et al., 2018). The instrument comprises six subscales: enjoyment, absorption, creative thinking, involvement, absence of negative effects, and dominance. The Turkish adaptation was validated and found reliable by Arıkan Dönmez et al. (2024). Scale scores range from 27 to 135, with higher scores indicating a more positive gaming experience. Cronbach's alpha was 0.93 for the total scale, and subscale alphas ranged from 0.67 to 0.929.

Qualitative data

Focus group discussions with students and facilitators were organized within one week after the completion of the HYPSEM game. The sessions were held via the Zoom video conferencing platform and followed a semi-structured interview form. Three female researchers with expertise in qualitative research served as moderators to ensure both consistency and depth

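### The game arm's post-test is tied to successfully exiting the game, and neither the protocol nor the SAP says how students who did not play or finish were tested or analysed

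*Combined protocol and SAP*

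**What the plan says.** All places are in the combined protocol and SAP.

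- **Game arm, procedure** (HYPSEM game procedure): students play alone over a week, "They were then given one week to play individually at their convenience". The last step is "After successfully completing the final test and exiting the escape room, students filled out a post-test questionnaire".
- **Game arm, stages** (Experimental procedure, Stage 2): "Upon completion, students’ knowledge and satisfaction were evaluated".
- **Game arm, schedule** (Implementation phase of the study, Intervention Group): "Immediately after the intervention and again one month later, students completed the Hypovolemic Shock Information Form as a posttest". No success condition appears here, but the same paragraph sends the reader to the Experimental procedure section for the game's procedures.
- **Control arm, schedule** (same section, Control Group): "Immediately after the lecture and again one month later, students completed the Hypovolemic Shock Information Form as a posttest".
- **Help during play** (HYPSEM game procedure; Escape room design): "Students could request unlimited hints and were reassured that feedback would be available even without prior experience", and "Students could replay the game without restriction during the one-week study period".
- **Numbers** (Setting and participants): "58 volunteer students were recruited for the quantitative phase and randomly assigned to either the intervention or control groups". The allocation ratio is 1:1. The arms are later shown as 27 (game) and 28 (control).
- **Analysis** (SAP): a repeated-measures ANOVA over the pre-test and two post-tests, plus a t-test between groups at each time. No analysis set and no missing-data method are named.

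**The concern.** The only trigger that the procedure gives for the game arm's post-test is a successful exit. A student who never opens the game, or who stops part-way, has no event that leads to post-test 1. The one-month test is counted from the intervention, so it has no start date for that student either. A standard repeated-measures ANOVA keeps only students with all three scores, so that student also leaves the main analysis.

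Whether a student finishes is settled after randomisation and plausibly reflects engagement, which also bears on the test score. Controls face no such step. If non-finishers are untested, the trial compares game finishers with controls who were not selected in this way. That is not the randomised comparison, and the expected direction of the error favours the game.

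**Working it through.** **1. The plan's own figure.** Inputs from Setting and participants: f = 0.35, three measurements, correlation 0.50, alpha 0.05, power 0.80. For the between-group effect, λ = f² × N × m / (1 + (m − 1)ρ).
- N = 46: λ = 0.1225 × 46 × 3 / 2 = 8.45, power 0.811.
- N = 44: λ = 8.08 (8.085 before rounding), power 0.793.

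So 46 is reproduced. For two equal groups f = 0.35 is d = 2 × 0.35 = 0.70 SD, which is the yardstick used below.

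**2. How many students could be involved.** 58 − (27 + 28) = 3 unaccounted for, with no arm or reason given. Two splits are considered, both assuming that 27 and 28 are the analysed numbers:
- A, 29:29 randomised: 2 lost from the game arm, 1 from control.
- B, 30:28 randomised: 3 lost from the game arm, none from control.

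**3. Tilt at one post-test.** Assume no true effect, normal scores in SD units, and that the lost game-arm students are those with the lowest tendency to finish. Let r be the assumed correlation of that tendency with the score. Then tilt = r × (mean of those who remain).
- A: expected lowest two of 29 are −2.03 and −1.60, so the remaining 27 average 3.63 / 27 = 0.134.
- B: expected lowest three of 30 are −2.04, −1.62 and −1.37, so the remaining 27 average 5.03 / 27 = 0.186.

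| Split | r = 0.3 | r = 0.5 | r = 1 (worst case) |
|---|---|---|---|
| A, 2 lost | 0.04 SD | 0.07 SD | 0.13 SD |
| B, 3 lost | 0.06 SD | 0.09 SD | 0.19 SD |

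In A the lost control is taken as unrelated to the score. If that control was also the lowest scorer, the worst-case tilt falls to 0.06 SD.

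**4. False claims in favour of the game.** Simulated t-test at one post-test with no true effect; nominal rate in this direction 2.5%.
- A: 3.5% (r = 0.3), 4.4% (r = 0.5), 8.2% (r = 1).
- B: 4.0% (r = 0.3), 5.4% (r = 0.5), 11.7% (r = 1).

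**5. Pre-to-post change.** A student dropped from the ANOVA loses the pre-test too, so part of the tilt cancels. Simulated with the protocol's correlation of 0.50 and r = 0.3 to 0.5:
- Finishing depends on stable ability: tilt in change is about 0, and the false-claim rate stays near 2.5%.
- Finishing depends directly on the post-test 1 score: tilt is 0.02 to 0.05 SD, about half of the single-test figure, and the rate is 3.0 to 3.7%.

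**6. A larger loss, as an assumption only.** With 6 of 30 lost (20%) and r = 0.3 to 0.5, the single-test tilt is 0.10 to 0.17 SD and the false-claim rate is about 5.6 to 9.2%. Nothing in the documents shows a loss of this size.

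**The case against.** The strongest reply is that the procedure reports a sequence and nowhere says that non-finishers were refused the test. The schedule, which names the knowledge form, has no success condition. The Stage 2 phrase may mean the end of the one-week stage. That much stands: exclusion is a reading of the text and not a recorded fact. It does not remove the point, because the schedule defers to the procedure, and no other trigger is given anywhere.

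Stronger readings are tempting, and the documents do not support them:
- **That weaker students were screened out.** Unlimited hints, technical support, free replay and a game without new content make finishing mainly a matter of engagement.
- **That students were lost from one arm only.** An exact 1:1 split of 58 against 27 and 28 means that one control was lost too. Only the loss caused by the exit condition is confined to the game arm.
- **That satisfaction and interview data come only from students who succeeded.** No success condition is stated for GAMEX. The 12 interviewed students were drawn from participants in the quantitative phase, and nurse educators were included as well.
- **That the bias is large.** That needs about 20% non-completion or a very strong correlation.

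It is also fair to say that the change-based comparison in the ANOVA is less exposed than the separate t-tests, and that part of the remedy coincides with explaining the gap between 58 and 55.

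**Conclusion.** The point holds as a gap in the plan: the game arm's post-test is tied to a successful exit, the control arm's is not, and no rule covers a student who does not play or finish. Following the text can produce loss related to the outcome, mainly through non-engagement, and that route exists only in the game arm.

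The size is small to modest. With two or three game-arm students lost and r of 0.3 to 0.5, it is about 0.04 to 0.09 SD at one post-test, and false claims in favour of the game run at about 3.5 to 5.5% against 2.5%. In pre-to-post change it is about half of that or nil. It could not by itself produce the planned 0.70 SD.

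These figures rest on three assumptions: the values of r, the lost game-arm students being those least inclined to finish, and 27 and 28 being analysed numbers. The documents do not say whether those counts are randomised or analysed. If more students lack post-tests within them, the tilt could be larger. A reader might infer that the trial is already a comparison of finishers with all controls; the documents do not establish that. This should be fixed, with moderate confidence.

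**What to change.** **In the plan.** Reconcile the Implementation phase section with the HYPSEM game procedure. State that every student randomised to the game arm takes post-test 1 on finishing the game, or at the end of the one-week access period if not finished, and post-test 2 one month later, whatever their game status. In the SAP, state that all students are analysed in the arm assigned. Record game status as not opened, opened but not exited, or exited.

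**If data are already collected** (the study is described as run in June and July 2025, so this may be all that remains possible):
- report by arm the numbers randomised, opened (game arm), exited (game arm) and tested, with the reasons for the three students unaccounted for;
- include any available scores from non-finishers;
- add a sensitivity analysis for missing scores;
- label any finisher-only result as such, including GAMEX if that applies.

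**Cost.** A few sentences, plus sending the form to all game-arm students. The estimated effect may be slightly smaller once non-players are included. Non-finishers would be tested up to a week after the lecture, while controls are tested straight after it. Keeping the test on finishing for those who do finish avoids delaying early finishers to the end of the week.
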